6.1.7. Subgroup Analyses

All data will be presented for the following subgroups, with the relevant analysis sets described in Table 3:

- **Treatment-naïve:** Patients in the All Treated Analysis Set who are naïve to HLH treatment (according to section 6.1.6).
- **Treatment-experienced:** Patients in the All Treated Analysis Set who have received conventional HLH therapy (as per site standard of care) without having obtained a satisfactory response according to the treating physician or having shown signs of intolerance to previous HLH therapy.

Conventional HLH therapy is defined as per site standard-of-care, e.g., any of the following, alone or in combination (etoposide, ATG, alemtuzumab and cyclosporine A) or glucocorticoids, namely dexamethasone at 10 mg/m^2 for at least 7 days or methylprednisolone pulses for 3 consecutive days.

Table 3: Patient Populations for Each Analysis/Summary

	Patient Populations						
	Enrolled	All Treated Analysis Set			Evaluable Analysis Set		
Analyses	Population Analysis Set	Treatment naïve	Treatment experienced	Total	Treatment naïve	Treatment experienced	Total
Patient Disposition	Х	Х	Х	Х	Х	Х	Х
Protocol Deviations	X*						
Demographics, Baseline		X	Х	Х			
Prior and Concomitant Therapies		X	Х	Х			
Primary Efficacy Endpoint		X	Х	Х	Х	Х	Х
Secondary Efficacy Endpoints		X	X	Х	Х	Х	Х
Sensitivity analysis 1: Overall Response at EOT or Week 8 (whichever occurs earlier) with deaths considered as non-responders		X	X	Х			
Sensitivity analysis 2: Overall Response at EOT or Week 8 (whichever occurs earlier) with early withdrawal considered as non- responders					Х	Х	Х
Sensitivity analysis 3: Overall Response at EOT or Week 8 (whichever occurs earlier) with patients who receive concomitant administration of other HLH treatments considered as non-responders		Х	Х	Х			

			Patient Populations				
	Enrolled	All Treated Analysis Set			Evaluable Analysis Set		
Analyses	Population Analysis Set	Treatment naïve	Treatment experienced	Total	Treatment naïve	Treatment experienced	Total
Sensitivity analysis 4: Overall Response at EOT or Week 8 (whichever occurs earlier) with deaths, early withdrawals, and patients who receive concomitant administration of other HLH treatment considered as non- responders		Х	Х	Х			
Sensitivity analysis 5: Overall Response at EOT or Week 8 (whichever occurs earlier) with patients deemed as having a major protocol deviation impacting statistical analysis removed from the Analysis Set					X^	X^	X^
Supplementary analysis: Overall Response at EOT or Week 8 (whichever occurs earlier) - Modified Definition		Х	Х	Х			
Exposure		Х	Х	Х			
Quality of life: PedsQL [™] , BASES		Х	Х	Х			
Safety: AEs, SAEs, Lab tests		Х	Х	Х			
Safety: Vital Signs, Physical Examination, ECG		Х	Х	Х			

* Excluding Screening failures ^ Evaluable Analysis Set Without Major Protocol Deviations

6.1.8. Pooling of Sites

As relatively few patients are expected in the study, the centers will not be taken into account in the analyses.

6.1.9. Derived Variables

6.1.9.1. General

• Sponsor defined study day = date of interest – date of first emapalumab infusion

[figure not shown]
Note: This study day will be used in the analysis visit windowing and displayed on listings if required. Study Day 0 (SD0) is the day when first emapalumab infusion is performed.

• Change from baseline = value at current time point – value at baseline.

6.1.9.2. Demography and Baseline Parameters

- Conversion factors: The following conversion factors will be used to convert days into months or years:
 - 1 month = 30.4375 days
 - 1 year = 365.25 days
- Age at diagnosis in years = date of diagnosis date of birth +1.
- Age in days = date of informed consent date of birth +1.
- Age in years = Age in days / 365.25.
- Age categories: The following groups will be used for categorizing age:

Age Group	Definition
Newborns (0-27 days)	$0 \le (Date of informed consent - Date of Birth +1) \le 27$
Infant and toddlers (28 days - 23 months)	$28 \le$ (Date of informed consent – Date of Birth +1) and age in years = 1
Children (2-11 years)	2 <= age in years <= 11
Adolescents (12-18 years)	12 <= age in years <= 18

[figure not shown]
6.1.9.3. Safety Parameters

Table 4: Definition of Drug Administration Variables

Statistics for Exposure (dosing)	Derivation
Duration of exposure (days)	Date of last infusion of emapalumab – date of first infusion of emapalumab + 1
Duration of exposure (weeks)	Duration of exposure (days)/7
Maximum dose prescribed	Maximum of all doses prescribed (mg/kg)
Cumulative dose (mg/kg)	Sum of total actual dose per kg administered from first infusion date until last infusion date
Average dose frequency (days)	Duration of exposure (days)/ total number of infusions
Average dose of emapalumab per day (mg/kg)	Cumulative dose (mg/kg)/ duration of exposure (days)
Percentage of dose increases from baseline dose	(Number of dose increases from baseline dose / number of total doses) multiplied by 100.
Percentage of dose decreases from baseline dose	(Number of dose decreases from baseline dose / number of total doses) multiplied by 100.

Table 5: Definition of Adverse Events

Variable	Definition
Adverse Event (AE)	All recorded AEs (collection of AEs starts after ICF signature).
Treatment-Emergent Adverse Event (TEAE)	Any AE (serious and non-serious) with an onset date after the start of the first emapalumab infusion.
Pre-conditioning AE	Any AE (serious and non-serious) with start date before the start of conditioning for HSCT*.

[figure not shown]

Variable	Definition			
Post-conditioning AE	Any AE (serious and non-serious) with start date after the start of conditioning for HSCT*.			
TEAEs related to the study drug	Any AEs with an onset date after the start of the first emapalumab infusion with "Relationship to Study Drug" of "Related".			
Serious TEAEs	Any AEs with an onset date after the start of the first emapalumab infusion with "Serious" of "Yes".			
TEAEs leading to withdrawal of study drug	Any AEs with an onset date after the start of the first emapalumab infusion with "Action taken with study drug" of "Drug Withdrawn".			
TEAEs resulting in death	Any AEs with an onset date after the start of the first emapalumab infusion with "Results in death" of "Yes".			
TEAE with infections	Any AE with an onset date after the start of the first emapalumab infusion with system organ class (SOC) 'Infections and Infestations' or in the HLGT 'Microbiology and serology investigations'.			
TEAE with infusion-related reactions (IRRs)	Any AE reported to have occurred within 24 hours after the start of infusion and reported as related to study treatment by the Investigator, excluding the following SOCs: "Infections and infestations," "Congenital familial and genetic disorders," "Neoplasms benign, malignant and unspecified (incl. cysts and polyps)," "Product issues," "Social circumstances," and "Surgical and medical procedures."			
	If the onset time of the AE or the start time of the infusion is missing, then an AE with an onset date equal to an infusion date or infusion date +1 will be considered for the assessment of IRRs, unless the available information clearly indicates the AE was not treatment-emergent.			

*Note: The start date of conditioning is captured in the HSCT module of the eCRF or CM module. For more information of HSCT medications see Appendix 16.2.

AD-ST-33.06 Effective date: 12-Nov-2020

[figure not shown]

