3.4 FOLLOW-UP PERIOD

After treatment completion or treatment discontinuation (for any reason), patients will continue in the study for long-term follow-up until 1 year after either HSCT or last emapalumab infusion (if HSCT is not performed).

Study NI-0501-09 NI-0501 in Primary HLH Page 31 of 92

If patient experiences HLH reactivation during the follow-up period, patient may be re-treated with emapalumab, upon discussion with Sponsor. Re-treated patient will follow the same schedule of assessments as applicable during initial treatment (i.e., starting from Visit 1), and will enter follow-up period after completion of re-treatment.

If the patient is unable to return to the site for all follow-up visits, every effort should be made to schedule visits until emapalumab is no longer detectable in the blood.

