3.4. Treatments Administered

This is an open-label, single-arm study and no randomization is being performed. Emapalumab will be administered by intravenous (IV) infusion over a period of 1 to 2 hours depending on the volume to infuse, at a dose of 3 mg/kg. Infusions will be performed twice weekly (not more than 4 days apart), except for the second infusion which must be administered on SD-3. The 3 mg/kg dose will be maintained unless the Investigator, guided by the clinical and laboratory response in each patient, deems that a dose increase is appropriate; at any time during the study, it will be possible to increase the emapalumab dose to 6 mg/kg. The dose of emapalumab may be further increased to 10 mg/kg per Investigator's decision based on the patient's clinical and laboratory response.

Upon achievement of Complete Response (i.e., normalization of all clinical and laboratory HLH parameters), the dose of emapalumab will be lowered to achieve 1 mg/kg twice a week and maintained until conditioning for transplant, as long as the patient's clinical conditions are satisfactory. Given the unpredictable course of the disease, in case of reactivation (e.g. triggered by intercurrent infections), subsequent dose increases to 3 mg/kg (and up to 6 or 10 mg/kg, as appropriate) may need to be considered and will be guided by the same clinical and laboratory parameters. Upon obtaining again a Complete Response, the dose of emapalumab will be lowered again to achieve 1 mg/kg twice a week. Should hematopoietic stem cell transplantation (HSCT) be scheduled beyond 12 weeks from emapalumab initiation for reasons unrelated to the administration of emapalumab (e.g., lack of donor availability) and provided Complete Response is maintained, the treatment with emapalumab may continue at the dose of 1 mg/kg once a week.

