6.1.5. Analysis Visit Windows

Statistical analyses will be based on the windowing displayed in Table 1 (patients with a

treatment duration less than 8 weeks, i.e. < 56 days) and Table 2 (patients with a treatment duration of 8 weeks or more, i.e. >= 56 days).

However, imputation of missing data will be applied as described in Section 6.1.4.

Visit Name		Tougot dou	Analysis visit window			
		Target day	From SD	To SD		
Baseline				ded prior to the first dose apalumab		
Study Day 0 (free mapal		1	1	1		
Study	Day 3	4	2	5		
Study Day x		Study Day x + 1 day	Target day – 1 day	Target day + 1 day		
	Study Day n-1	Study Day x +1 day	Target day – 1 day	Day of last infusion of emapalumab		
a) EOT visit available	EOT / Week 8	EOT visit	Day of last infusion of emapalumab +1	EOT visit		
	EOT	EOT visit	EOT visit	EOT visit		
	Study Day n-1	Study Day x +1 day	Target day – 1 day	Day of last infusion of emapalumab – 1 day		
b) no EOT visit available	EOT / Week 8	Start day of last infusion *	Start day of last infusion *	End day of last infusion *		
	EOT	Start day of last infusion *	Start day of last infusion *	End day of last infusion *		

[figure not shown]
* Start and End date of infusion are in most of the cases the same date.

- a) If an EOT visit was performed and treatment duration was < 8 weeks (i.e. < 56 days), the day of EOT visit will be assigned as EOT/Week 8 analysis visit and as EOT visit prior to start of conditioning.
- b) If no EOT visit was performed and treatment duration was < 8 weeks (i.e. < 56 days), the day of last infusion will be assigned as EOT/Week 8 analysis visit and as EOT visit prior to start of conditioning.

		-	Analysis visit window			
Visit Name		Target day				
			From SD	To SD		
Baseli	ne		Last observation recorded prior to the first dose of emapalumab			
Study Day 0 (firs	t infusion of	1	1	1		
emapalur		1	1	1		
Study D	ć	4	2	5		
Study D	•	7	6	8		
Study D	•	10	9	11		
Study Da	2	13	12	14		
Study Da	2	16	15	17		
Study Da		19	18	20		
Study Da	•	22	21	23		
Study Da		25	24	26		
Study Da		28	27	29		
Study Da		31	30	32		
Study Da		34	33	35		
Study Da	•	37	36	38		
Study Da	2	40	39	41		
Study Day 37 Study Day 42		43	42	44		
Study Da	•	46	45	47		
Study Day 49 Study Day 48		49	48	50		
Week 8 is the last week prio			_	20		
	Study Day 51	52	51	Day of last infusion of emapalumab		
a) EOT visit available	EOT / Week 8	EOT visit	Day of last infusion of emapalumab + 1 day	EOT visit		
	EOT	EOT visit	EOT visit	EOT visit		

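### SAP Table 4 understates the mean dosing interval and counts off-drug months as exposure in re-treated patients (descriptive tables only)

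*SAP*

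**What the plan says.** Table 4 in SAP section 6.1.9.3 sets out four linked exposure variables:

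- Duration of exposure in days: "Date of last infusion of emapalumab – date of first infusion of emapalumab + 1".
- Average dose frequency in days: "Duration of exposure (days)/ total number of infusions".
- Cumulative dose: "Sum of total actual dose per kg administered from first infusion date until last infusion date".
- Average dose per day: the cumulative dose divided by that duration.

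SAP section 7.4 summarises all four and describes duration as running from the first to the last dose. It makes no mention of treatment courses.

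On schedule, SAP section 3.4 says "Infusions will be performed twice weekly (not more than 4 days apart"), with the second infusion at a fixed time. The starting dose is covered by "The 3 mg/kg dose will be maintained unless the Investigator" judges an increase appropriate.

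On re-treatment, Protocol section 3.4 says "If patient experiences HLH reactivation during the follow-up period, patient may be re-treated with emapalumab, upon discussion with Sponsor". Protocol section 5.3 and SAP section 3.1 repeat the provision, and re-treated patients restart the schedule of assessments from Visit 1. The only output specific to re-treatment is in SAP section 7.1: a tabulation of how many patients were re-treated and how many re-treatment periods each had.

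**The concern.** Two features of Table 4 do not measure what their labels say.

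First, the interval formula divides by the number of infusions, not by the number of gaps between them. The result is always too short when the true mean interval exceeds one day, and the error is largest in short courses. It can also hide a late infusion. Infusions on study days 0, 3 and 9 have a mean interval of 9/2 = 4.5 days, which shows that at least one gap exceeded 4 days. Table 4 reports 10/3 = 3.33 days, which looks compliant.

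Second, first-to-last duration spans any off-drug period between an initial course and re-treatment. Every variable that uses duration is then distorted.

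What is at stake is the accuracy of the exposure summary in the study report. The primary analysis is not affected.

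**Working it through.** The documents report no values for these variables, so there is no plan figure to reproduce. The check applies the Table 4 formulas to schedules built from the plan's own dosing rule.

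**Inputs.** Formulas: SAP Table 4. Schedule: twice weekly, taken as alternating gaps of 3 and 4 days (an assumption; a strict 3-day grid is the alternative). Dose: constant 3 mg/kg, for illustration, so the nominal rate is 3/3.5 = 0.857 mg/kg/day. Length of the off-drug gap and number of re-treated patients: not given. A gap of 30 to 180 days is assumed, counted from the last infusion of one course to the first of the next.

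**Interval, single course.** Let m = (last − first)/(n − 1). Table 4 gives [(n − 1)m + 1]/n = m − (m − 1)/n. This holds for any spacing.

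| n | last − first | Table 4 | true mean |
|---|---|---|---|
| 1 | 0 | 1/1 = 1 | none exists |
| 3 | 7 | 8/3 = 2.67 | 7/2 = 3.5 |
| 8 | 24 | 25/8 = 3.13 | 24/7 = 3.43 |
| 16 | 52 | 53/16 = 3.31 | 52/15 = 3.47 |
| 52 | 178 | 179/52 = 3.44 | 178/51 = 3.49 |

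On a strict 3-day grid the values are 2.33 against 3 days at n = 3, and 2.88 against 3 at n = 16. The case n = 1 can occur, because the All Treated Analysis Set admits anyone who received any part of an infusion.

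**Daily dose, single course.** The last dose is counted in full with only one day of time attached. Against 0.857 mg/kg/day:

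- n = 3: 9/8 = 1.125 (+31%)
- n = 8: 24/25 = 0.960 (+12%)
- n = 16: 48/53 = 0.906 (+5.7%)
- n = 52: 156/179 = 0.872 (+1.7%)

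Measured against the dose divided by the course's own mean interval, the excess is slightly smaller. At n = 8 it is 0.960/(3/3.429) = 0.960/0.875, or +10%. At n = 16 it is 0.906/0.865, or +5%.

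**Re-treated patient: 16 infusions, 180-day gap, 8 infusions.**

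- Table 4 duration: 52 + 180 + 24 + 1 = 257 days. Summed over courses: 53 + 25 = 78 days.
- Table 4 interval: 257/24 = 10.7 days. Within courses: (52 + 24)/(15 + 7) = 3.45 days.
- Table 4 daily dose: 72/257 = 0.28 mg/kg. Over the summed courses: 72/78 = 0.92 mg/kg.

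Using the SAP's month of 30.4375 days, the 6-month treatment limit is about 183 days. The 257-day figure would therefore look like an overrun in a patient treated for 78.

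**Sensitivity to the gap: two courses of 8 infusions, 50 days summed.**

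| gap (days) | Table 4 duration (days) | Table 4 interval (days) | Table 4 daily dose (mg/kg) |
|---|---|---|---|
| 30 | 79 | 4.9 | 0.61 |
| 60 | 109 | 6.8 | 0.44 |
| 90 | 139 | 8.7 | 0.35 |
| 180 | 229 | 14.3 | 0.21 |

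The summed-course daily dose is 48/50 = 0.96 mg/kg throughout. The direction of error in daily dose therefore reverses: too high within one course, too low across a gap.

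**The case against.** The strongest reply is that these are openly stated descriptive conventions with small effects. For a course of 16 infusions the interval is off by about 0.16 days, and the larger discrepancies need very short courses, whereas the plan foresees at least 4 weeks of treatment where transplant is feasible. SAP section 7.4 also lists every administration and every dose change, so the raw facts remain visible. This limits the severity, but it does not make the interval formula correct, and it does not answer the re-treatment problem, where the distortion is several-fold.

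A reader might infer two stronger consequences.

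- **That the primary endpoint is misplaced.** SAP section 6.1.5 chooses between its window tables by "treatment duration less than 8 weeks, i.e. < 56 days" or longer. If that were Table 4 duration over all courses, a patient with a short first course and later re-treatment would be assessed around day 57, possibly off drug. The documents do not support reading it that way. Section 6.1.5 does not cite Table 4. SAP section 3.1 uses the term treatment duration for the treatment period and places re-treatment under follow-up. The endpoint is taken at the earlier of end of treatment and Week 8. Protocol section 8.5 provides only an end-of-treatment visit when treatment finishes before Week 8. What remains is an undefined term that deserves one clarifying sentence.
- **That the assessment of the 3 mg/kg starting dose rests on average daily dose.** That assessment is a study objective, but no section ties it to this variable. Section 7.4 also supplies dose increases by visit, with dose levels and reasons.

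**Conclusion.** The point holds and is minor. As written, Table 4 understates the mean dosing interval by (m − 1)/n and returns a meaningless 1 day for a single infusion. In re-treated patients it counts the off-drug gap as exposure, which overstates duration and interval and understates daily dose. Single-course daily dose is modestly overstated, by about 12% at 8 infusions and 6% at 16 against the nominal rate.

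The algebra for the interval needs no assumption. The worked figures assume alternating 3- and 4-day gaps and a constant 3 mg/kg, and the re-treatment figures also assume the gap length. How many patients are affected by re-treatment cannot be judged from the documents. None of these variables enters the primary test.

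**What to change.** Edit SAP Table 4 and section 7.4:

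1. Define the average dosing interval as (last − first)/(n − 1) within a treatment course, not calculable when n = 1. If one value per re-treated patient is wanted, divide the summed within-course spans by the summed within-course intervals.
2. Compute duration of exposure and average daily dose for each course and summed over courses, leaving out off-drug gaps. Show the initial course separately from the total.
3. For clarity only, state in section 6.1.5 that treatment duration, end of treatment and Week 8 refer to the initial course. This agrees with the existing endpoint definition.

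The modest single-course excess in daily dose remains after these changes. Extending the denominator beyond the last infusion is a matter of convention, complicated by the possible move to weekly dosing after 12 weeks, and is not requested here.

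The cost is a text edit to the SAP and the matching derivation code. No new data are needed, and the hypothesis test does not change.

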6.1.9.4. Efficacy Parameters

- Overall Response at EOT or Week 8 = achievement (yes/no) of either Complete or Partial Response or HLH improvement at EOT or the Week 8 assessment, whichever occurs earlier.
- Overall Response at start of conditioning for HSCT = achievement (yes/no) of either Complete or Partial Response or HLH improvement at start of conditioning of HSCT (date of start of conditioning) or last emapalumab if HSCT is not performed.

The definition of the Overall Response for the primary endpoint is detailed in Table 6 along with additional clarifications.

The definition of the Overall Response used in the supplementary analysis is detailed in Table 7.

Response for Primary Endpoint	Definition	Additional Clarifications
Complete Response	Complete Response is adjudicated if: - No fever = body temperature < 37.5 °C - Normal spleen size - No cytopenia = Absolute Neutrophil Counts $\geq 1.0 \times 10^{9}$ /L and platelet count $\geq 100 \times 10^{9}$ /L [absence of G-CSF and transfusion support must be documented for at least 4 days to report no cytopenia] - No hyperferritinemia = serum ferritin level is < 2000 µg/L - No evidence of coagulopathy, i.e., normal D-Dimer and/or normal (> 150 mg/dL) fibrinogen levels - No neurological and CSF abnormalities attributed to HLH - No sustained worsening of sCD25 (as indicated by at least two consecutive measurements that are > 2-fold higher than baseline)	 All HLH parameters that were abnormal at baseline must be normalized No AEs relating to organ failure All other parameters that were normal at baseline must still meet the definition of normalized Normal spleen size confirmed by abdominal ultrasound (US) whenever possible based on the splenomegaly not present; if US not performed physical examination will be used Normal D-Dimer levels are <= 500 ug/L No neurological abnormalities attributed to HLH = "normal" neurological assessment by investigator in the neurological examination page (without findings in brain imaging (Brain MRI/Brain CT/cranial ultrasound) or AEs indicative of "CNS involvement" (Appendix 15.3) No CSF abnormalities = no AE indicative of "CSF abnormalities" (Appendix 15.3)

[figure not shown]
Response for Primary Endpoint	Definition	Additional Clarifications
Partial Response	 Partial Response is adjudicated if: At least 3 of the HLH clinical and laboratory abnormalities (including CNS abnormalities) meet the above mentioned criteria for "Complete Response" In the case of "reactivated patients" who enter the study with 3 abnormal HLH features, Partial Response is adjudicated if at least 2 parameters normalize 	If a patient is not considered as "reactivated" or a patient is considered "reactivated" with 4 or more abnormal HLH features upon entry to the study and at least 3 of the HLH clinical and laboratory abnormalities (including CNS abnormalities) meet the above-mentioned criteria for "Complete Response" Partial Response is adjudicated.
	 In case of reactivated patients who enter the study with 2 abnormal HLH clinical and laboratory parameters only, Partial Response is adjudicated if one of the 2 parameters normalizes There is no progression of other aspects of HLH disease pathology 	For all patients: no progression of other aspects of HLH disease pathology is assessed by absence of AEs indicating organ failure including no worsening of sCD25 levels.

Response for Primary Endpoint	Definition	Additional Clarifications
HLH Improvement	 HLH Improvement is adjudicated if: Improvement (>50% change from baseline or normalization) of at least 3 HLH clinical and laboratory abnormalities (including CNS abnormalities). In the case of "reactivated patients" who enter the study with only 2 abnormal HLH features, a change from baseline greater than 50% for both will define HLH as improved. 	 Definition of 50% improvement from baseline: Spleen size decreased by 50%, as recorded in cm from costal margin at physical examination. Absolute Neutrophil Count increased by 50%, if G-CSF has not been administered in the previous 4 days and Platelet count increased by 50%, if no platelet transfusion has been administered in the previous 4 days Ferritin decreased by 50% Fibrinogen increased by 50% or D-Dimer decreased by 50% Normalization of CNS abnormalities = normal neurological assessment by investigator without findings in brain imaging (Brain MRI/Brain CT/cranial ultrasound), CSF analysis or AEs indicative of "CNS involvement" or "CSF abnormalities"
No Response	If a subject does not meet the criteria for at least HLH improvement, response is categorized as "No Response"	
Abbreviations: CNS, c lymphohistiocytosis	entral nervous system; CSF, cerebrospinal fluid; G-CSF, gr	anulocyte-colony-stimulating factor; HLH, hemophagocytic

AD-ST-33.06 Effective date: 12-Nov-2020

Version 2.0 | Date 24-Oct-2022 | AD-PR-109.02 Effective date: 17-Aug-2020

Response for Supplementary Analysis	Definition	Additional Clarifications
Complete Response	Complete Response is adjudicated if: - No fever = body temperature < 37.5 °C - Normal spleen size - No cytopenia = Absolute Neutrophil Counts $\geq 1.0 \times 10^9/L$ and platelet count $\geq 100 \times 10^9/L$ [absence of G-CSF and transfusion support must be documented for at least 4 days to report no cytopenia] - No hyperferritinemia = serum ferritin level is < 2000 µg/L - No evidence of coagulopathy, i.e., normal D-Dimer and/or normal (> 150 mg/dL) fibrinogen levels - No neurological and CSF abnormalities attributed to HLH - No sustained worsening of sCD25 (as indicated by at least two consecutive measurements that are > 2-fold higher than baseline)	 All HLH parameters that were abnormal at baseline must be normalized No AEs relating to organ failure All other parameters that were normal at baseline must still meet the definition of normalized Normal spleen size confirmed by abdominal ultrasound (US) whenever possible based on the splenomegaly not present; if US not performed physical examination will be used Normal D-Dimer levels are <= 500 ug/L No neurological abnormalities attributed to HLH = "normal" neurological assessment by investigator in the neurological examination page (without findings in brain imaging (Brain MRI/Brain CT/cranial ultrasound) or AEs indicative of "CNS involvement" (Appendix 15.3) No CSF abnormalities = no AE indicative of "CSF abnormalities" (Appendix 15.3)

Table 7: Definition of Response for Supplementary Analysis

Response for Supplementary Analysis	Definition	Additional Clarifications
